#### WEEK 11 (OPTIONAL)

- Physical examination including your signs (blood pressure, pulse, and breathing rate) weight and height, and amount of oxygen in the blood
- Blood collection for safety labs (complete blood count, electrolytes, liver function and renal function (CMP, CBC+diff, c-reactive, carboxy hemoglobin, and PT/PTT).

#### **WEEK 12**

- Physical examination including your signs (blood pressure, pulse, and breathing rate) weight and height, and amount of oxygen in the blood
- Lung function tests (lung volumes, spirometry (post bronchodilator))
- Assessment of any side effects or symptoms and if there have been any changes in any of the medications you may be taking
- EKG
- Blood will be drawn from a vein to check blood counts (to look for infection or anemia), blood chemistries (blood minerals, blood sugar level, kidney and liver function), stored serum and biomarkers
- Urine will be collected to measure the break-down product of nicotine from cigarette smoke, for substances released from cells that are involved in inflammation, PGE collection, and to evaluate toxicology for drugs
- For females capable of getting pregnant, urine will be collected to test for pregnancy. If you are pregnant, you will not be allowed to participate in this study
- Study drug dispensing
- Oral rinse to collect samples of the bacterial communities in the oral mouth and upper airway and to remove loose debris that may contaminate the airway samples.
- Bronchoscopy

#### **WEEK 18**

- Physical examination including your signs (blood pressure, pulse, and breathing rate) weight and height, and amount of oxygen in the blood
- Assessment of any side effects or symptoms and if there have been any changes in any of the medications you may be taking
- Blood will be drawn from a vein to check blood counts (to look for infection or anemia), blood chemistries (blood minerals, blood sugar level, kidney and liver function), stored serum and biomarkers
- Urine will be collected to measure protein levels, check kidney function, measure poisonous alkaloid from tobacco and the break-down product of nicotine from cigarette smoke
- For females capable of getting pregnant, urine will be collected to test for pregnancy. If you are pregnant, you will not be allowed to participate in this study
- Study drug dispensing

#### **WEEK 24**

• Physical examination including your signs (blood pressure, pulse, and breathing rate) weight and height, and amount of oxygen in the blood

- Lung function tests (lung volumes, spirometry (post bronchodilator) and diffusing capacity of the lung for carbon monoxide [DLCO])
- Assessment of any side effects or symptoms
- Blood will be drawn from a vein to check blood counts (to look for infection or anemia), HIV viral load (amount of virus in the blood), CD4 (T-cell) count, and blood chemistries (blood minerals, blood sugar level, kidney and liver function, CMP, CBC+diff, c-reactive and carboxy hemoglobin), stored serum and biomarkers.
- For females capable of getting pregnant, urine will be collected to test for pregnancy. If you are pregnant, you will not be allowed to participate in this study

#### Weill Cornell Doxycycline for COPD in HIV-Infected Patients

#### Table I: Schedule of Evaluations

	SCREENING	PRE-ENTRY	ENTRY	WK	WK	WK 11	WK	WK 18	WK 24	PREMATURE
		(OPTIONAL)		2	6	(OPTIONAL)	12			DISCONTINUATION
Informed consent, medical	Х									
history										
Clinical Assessments 	Х	Х	$X^*$	Х	Х	Х	$X^*$	Х	Х	Х
Safety labs 	X	Х	$X^*$	Х	Х	Х	$X^*$	Х	Х	Х
Blood test 	X	Х	X*			Х	$X^*$			
Other labs 	X									
HIV viral load	Х						Х		Х	Х
CD4 (T-cell) count	Х						Х		Х	Х
Research blood (collection priority) 			Х	Х	Х		Х	Х	Х	
Pregnancy test (urine)	X	Х	Х	Х	Х		Х	Х	Х	
Urine toxicology (drug panel)	Х		Х				Х			
PGE urine collection 	X**						X**			
Urinanalysis 	Х									
Urine Metabolites 	X		Х				Х	Х		
Spirometry	X		Х				Х		Х	Х
EKG	X		Х				Х			
Bronchoscopy 			Х				Х			
High resolution chest CT 		Х	X*							
Oral rinse 			Х				Х			
Respiratory (CAT)/smoking questionnaires			Х		Х		Х		Х	Х
Dispense study drug			Х		Х		Х	Х		
Pill count/adherence questionnaire				X	Х		Х	X	Х	X

\* Optional procedures if procedures were already conducted during the optional visits.

 Clinical assessments include full physical examination at screening, targeted physical examinations at other visits, ongoing assessments for adverse events and new clinical diagnoses and CAT review at each visit.

 Safety labs consist of complete metabolic panel, complete blood count, electrolytes, liver function and renal function (CMP, CBC+diff, c-reactive, carboxy hemoglobin).
  PT/PTT blood test

 Other Labs (Hepatitis panel (A, B and C), alpha-1 anti-trypsin, IgE)

Weill Cornell	Investigational New Drug Application
Doxycycline for COPD in HIV-Infected Patients	Clinical Protocol

Research blood: Bronchoscopy visits (Week 0/Entry and Week 12), blood samples are collected for: doxycycline blood levels, EMP, DNA, serum (doxycycline assay, biomarker assay, DGM biobank), and monocytes. Non-bronchoscopy visits: (Week 2, Week 6, and Week 18 and Week 24) blood samples are collected for: doxycycline blood levels and serum for (doxycycline assay, biomarker assay and DGM biobank). Serum for biomarker assay will be frozen at -80°C for future assays (hsCRP, IL-6, TNF- $\alpha$ , IL-1 $\beta$ , procalcitonin). Should subject pre-maturely discontinue from the study, the subject will be invited to at least provide blood samples for the doxycycline blood assay.  Prostaglandin E urine collection, 9 mL. \*\*All subjects will be assessed for eligibility. PGE will be collected for any subject, who passes the screening as per the PI's recommendation, and has not taken NSAIDS within the past 7 days. Otherwise, subject will not be eligible for the PGE urine collection.

 Urine analysis will be collected to measure protein levels and kidney functions

 Urine metabolites will be collected to measure poisonous alkaloid from tobacco and the break-down product of nicotine from cigarette smoke

 Bronchoalveolar lavage;  $\geq$  50mL. To minimize any risk of bleeding to a subject after completion of the bronchoscopy procedure, subjects are advised not to take non-steroidal anti-inflammatory drugs (NSAIDs), such as aspirin and/or ibuprofen, for up to 7 days post-procedure.

 CT-scans taken within the last 6 months may be acceptable. Subjects will not be asked to complete more than 2 HRCT scans in one year If subjects complete the maximum of two HRCT scans in one year, they will receive no more than 2200mrem of radiation, which is within the guidelines for radiation exposure for human subjects; it is also below the maximum permissible dose limits per year for radiation workers according to the Nuclear Radiation Committee (5000mrem/year).

 Oral rinse to collect samples of the bacterial communities in the oral mouth and upper airway and to remove loose debris that may contaminate the airway samples. Subjects will be asked to cough 5 times and then actively gargle 10 cc of sterile saline for 20 seconds. At the end of the gargle, the subject will be instructed to swish the saline in the mouth for 5 seconds. The subject will then spit the oral rinse into the ORAL specimen container, gently spitting into the RNALater.

 Refer to Table II for the acceptable "time windows" for the assessment days.

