#### **Table II: Assessment Windows**

EVALUATION	SCREENING	PRE-ENTRY (Optional)	ENTRY	WK 2	WK 6	WK 11 (Optional)	WK 12	WK 18	WK 24	PREMATURE DISCONTINUATION
All other	N/A	N/A	N/A	±7	±7	N/A	N/A	±7	±7	±7 days
evaluations				days	days			days	days	
Bronchoscopy	N/A	N/A	±14 days	N/A	N/A	N/A	±14	N/A	N/A	N/A
Visits							days			

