#### **Table III: Bodily Fluid Collection**

Bodily Fluid	Amount	Number of Visits	Total (mL)
	(mL per test)		(To be taken over the course of 24 weeks)
Blood			
Doxycycline blood levels	12	6	72
Safety labs	36	6	216
Blood Test	3	2	6
Other lab	21	1	21

Weill Cornell Doxycycline for COPD in HIV-Infected Patients			Investigational New	Drug Application Clinical Protocol
HIV viral load	7	3	21	
CD4 (T-cell) count	4	3	12	
Serum for biomarkers	18	4	72	
Research blood	76	2	152	
Total			572	
Urine				
Urine Toxicology	12	3	36	
Pregnancy	7	8	56	
PGE Collection	9	2	18	
Urinalysis	10	1	10	
Urine Metabolites	4	2	8	
Total			128	
BAL fluid Total	50*	2	100	
Oral rinse Total	10	2	20	

\*Administer 150mL fluid up to 300 mL max, for a minimum return of 50mL

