#### 8.2. Subject Inclusion Criteria

- Males/Females ages 18-85 years
- Documented HIV infection
- CD4 cell count greater than 200 cells/mm3
- HIV RNA less than 400 copies/ml
- Stable antiretroviral therapy for greater than or equal to 12 weeks
- Fulfills GOLD definition for COPD (post-bronchodilator FEV1/FVC less than 0.7) and/or has radiographic evidence of emphysema
- Current or history of smoking with minimum 3 pack-year history
- ALT and AST less than 3 x upper limit of normal
- For women of childbearing potential: willingness to use 2 forms of birth control
- Subjects on therapy for COPD must be on stable therapy for at least 4 weeks

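### Table I gives women who complete the study a pregnancy test at the end of dosing, but schedules none for women who stop early

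*Combined protocol and SAP*

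**What the plan says.** - **Test schedule.** The Table I row "Pregnancy test (urine" has eight marks: Screening, optional Pre-Entry, Entry, and Weeks 2, 6, 12, 18 and 24. It is blank at optional Week 11 and at Premature Discontinuation.
- **Visit lists.** The lists in Section 7.2 agree with that row. The Week 24 list still states: "For females capable of getting pregnant, urine will be collected to test for pregnancy". There is no list for a discontinuation visit.
- **Dispensing.** The row "Dispense study drug" is marked at Entry and Weeks 6, 12 and 18, and not at Week 24.
- **What discontinuation does include.** Clinical assessments are marked there, and footnote 1 says that these cover "ongoing assessments for adverse events and new clinical diagnoses". Footnote 5 adds: "Should subject pre-maturely discontinue from the study, the subject will be invited to at least provide blood samples for the doxycycline blood assay".
- **Reproductive precautions.** Section 8.2 requires: "For women of childbearing potential: willingness to use 2 forms of birth control". Section 11.1 labels doxycycline category D, but also reports an expert review that thought a substantial teratogenic risk unlikely at therapeutic doses.

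**The concern.** The schedule tests women of childbearing potential at every main visit, including the last one, when treatment is over. A woman who stops treatment before Week 24 also ends her exposure, and the plan gives her a discontinuation visit with most of the Week 24 procedures, but not this test. A pregnancy that began since her last scheduled test and is not yet recognised would go undetected at exit. What is at stake is a small piece of safety information for the woman herself. No efficacy or safety analysis depends on it.

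**Working it through.** **1. Is the blank cell an isolated gap?** Nine rows of Table I are marked at Week 24: clinical assessments, safety labs, viral load, CD4 count, research blood, pregnancy test, spirometry, CAT/smoking questionnaires, and pill count/adherence. At Premature Discontinuation seven of these are marked, that is, all except research blood and the pregnancy test. Footnote 5 covers research blood at discontinuation. So 9 − 7 − 1 = 1 row has neither a mark nor a covering footnote, and it is the pregnancy test.

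**2. Does Table III help to decide whether the cell is meant to be blank?** The budget in "Table III: Bodily Fluid Collection" is 8 tests × 7 mL = 56 mL, which matches the eight marks. This does not confirm the blank, because Table III does not count the discontinuation column: viral load and CD4 each have four marks in Table I (Screening, Week 12, Week 24, discontinuation) but three visits in Table III. The better support is that the rest of the row agrees with the visit lists and that nothing elsewhere adds a test.

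**3. How old can the last test be?** The inputs are the Table I visit weeks and "Table II: Assessment Windows" (±7 days at Weeks 2, 6, 18 and 24; ±14 days at Week 12, which is a bronchoscopy visit). The longest interval is the latest day of the next visit minus the earliest day of the previous one.

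| Interval | Nominal | With windows |
|---|---|---|
| Week 2 to 6 | 4 weeks | day 49 − day 7 = 42 days |
| Week 6 to 12 | 6 weeks | day 98 − day 35 = 63 days |
| Week 12 to 18 | 6 weeks | day 133 − day 70 = 63 days |
| Week 18 to 24 | 6 weeks | day 175 − day 119 = 56 days |

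Entry to Week 2 is nominally 2 weeks. It is at most 21 days counted from day 0, or 21 + 14 = 35 days if the Entry window is used in full. So a woman who leaves between visits has a last test up to 6 weeks old nominally and up to 63 days old with the windows, provided that she missed no visit. If she missed Week 18, for example, the nominal limit becomes 24 − 12 = 12 weeks.

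**4. What would the added test change?** Table II gives the discontinuation visit ±7 days. It does not state the reference date, which I take to be the date of leaving. On that reading the last test would lie within 7 days of leaving.

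**5. How many women?** The documents give neither the number of women of childbearing potential nor a dropout rate, so any count is an assumption. If 10–30% of the 30 subjects are such women and 10–20% of them leave early, the count runs from 30 × 0.10 × 0.10 = 0.3 to 30 × 0.30 × 0.20 = 1.8. Of these, a share of 20/30, or 0.2 to 1.2, would be on doxycycline.

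**The case against.** The strongest reply is that no stated rule is broken. The only purpose that the visit lists give for the test is participation: a pregnant woman may not take part. A woman who has left is no longer taking part, and the sentence may simply have been copied into the Week 24 list. This stands in part: the documents nowhere announce a policy of testing at exit. But a test at Week 24 cannot control further dosing, because no drug is dispensed then. Whatever the intention, the schedule as written tests completers when dosing ends and does not test early leavers.

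There is also partial cover. A pregnancy already recognised at discontinuation can be recorded through the clinical assessments, and a clinician may test at discretion. That is fair, and it leaves only the unrecognised pregnancy.

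Three stronger readings are tempting, and the documents do not support them.

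- A reader might infer that the added mark would secure follow-up of birth defects, which Section 12.1.2a lists as a serious outcome, beyond the 30-day awareness period in Section 12.1e. It would not. The protocol sets out no pregnancy-reporting or outcome follow-up procedure, and a urine test at exit adds detection only.
- A reader might take 63 days as a firm maximum. It holds only if every visit is attended within its window.
- A reader might take 0.3 to 1.8 as missed pregnancies. It is an upper bound, under assumed percentages, on missing tests. It includes women who leave just after a scheduled test and women who would not come to the discontinuation visit, and it carries no probability of pregnancy.

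**Conclusion.** The gap is real but minor. Table I omits, for early leavers, the one Week 24 procedure that has neither a discontinuation mark nor a footnote, and gives no reason. The last test is then nominally up to 6 weeks old, up to 63 days with the windows if no visit is missed, and older otherwise. No hazard is shown: the protocol's own risk section regards substantial teratogenic risk as unlikely, and few women are likely to be affected in a study of 30. The sample size, the power and the primary safety endpoint do not depend on it. The conclusion rests on reading Week 24 as the end of dosing, which follows from six months of treatment and no dispensing at that visit. This is an optional improvement to the schedule.

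**What to change.** In Table I, mark the urine pregnancy test at Premature Discontinuation, for women of childbearing potential. Nothing else needs to change; footnote 5 already deals with the research blood.

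The cost is one 7 mL urine test per such woman who attends, at a visit already planned for safety labs, viral load, CD4 count and spirometry. An early leaver misses at least the Week 24 test, so she has at most 7 scheduled tests (Screening, Pre-Entry, Entry, Weeks 2, 6, 12 and 18) plus this one: 7 + 1 = 8 tests, and 8 × 7 = 56 mL. The Table III figure is not exceeded, and no extra blood is drawn.

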#### **Table II: Assessment Windows**

EVALUATION	SCREENING	PRE-ENTRY (Optional)	ENTRY	WK 2	WK 6	WK 11 (Optional)	WK 12	WK 18	WK 24	PREMATURE DISCONTINUATION
All other	N/A	N/A	N/A	±7	±7	N/A	N/A	±7	±7	±7 days
evaluations				days	days			days	days	
Bronchoscopy	N/A	N/A	±14 days	N/A	N/A	N/A	±14	N/A	N/A	N/A
Visits							days			

#### **Table III: Bodily Fluid Collection**

Bodily Fluid	Amount	Number of Visits	Total (mL)
	(mL per test)		(To be taken over the course of 24 weeks)
Blood			
Doxycycline blood levels	12	6	72
Safety labs	36	6	216
Blood Test	3	2	6
Other lab	21	1	21

Weill Cornell Doxycycline for COPD in HIV-Infected Patients			Investigational New	Drug Application Clinical Protocol
HIV viral load	7	3	21	
CD4 (T-cell) count	4	3	12	
Serum for biomarkers	18	4	72	
Research blood	76	2	152	
Total			572	
Urine				
Urine Toxicology	12	3	36	
Pregnancy	7	8	56	
PGE Collection	9	2	18	
Urinalysis	10	1	10	
Urine Metabolites	4	2	8	
Total			128	
BAL fluid Total	50*	2	100	
Oral rinse Total	10	2	20	

\*Administer 150mL fluid up to 300 mL max, for a minimum return of 50mL

#### 8. SELECTION AND WITHDRAWAL OF SUBJECTS

#### 8.1. Sample Population

Recruitment will be from the referral base of the responsible investigator and other physicians in the Division of Pulmonary and Critical Care Medicine, the NYPH Center for Special Studies (HIV clinic), and from community providers within the NY area.

#### 8.2. Subject Inclusion Criteria

- Males/Females ages 18-85 years
- Documented HIV infection
- CD4 cell count greater than 200 cells/mm3
- HIV RNA less than 400 copies/ml
- Stable antiretroviral therapy for greater than or equal to 12 weeks
- Fulfills GOLD definition for COPD (post-bronchodilator FEV1/FVC less than 0.7) and/or has radiographic evidence of emphysema
- Current or history of smoking with minimum 3 pack-year history
- ALT and AST less than 3 x upper limit of normal
- For women of childbearing potential: willingness to use 2 forms of birth control
- Subjects on therapy for COPD must be on stable therapy for at least 4 weeks

#### 8.3. Subject Exclusion Criteria

- Pulmonary infection, COPD exacerbation, or acute opportunistic infection within 30 days of entry
- Conditions associated with increased sedation of bronchoscopy risk, including but not limited to Gold class 3 or 4 COPD, requirement for home oxygen, hypercapneic respiratory failure, poorly control hypertension
- Known allergy/intolerance to doxycycline, atropine, or any local anesthetic
- Inability to provide informed consent
- Pregnant or lactating women
- Men must agree not to attempt to make a woman pregnant of participate in sperm donation during the study and for 6 weeks after discontinuing the drug
- End stage renal disease
- Cirrhosis
- INR greater than 1.4
- Platelets less than 80,000
- Any condition including active drug or alcohol use or dependence that, in the opinion of the site investigator, would interfere with adherence to study requirements or increase the risk of bronchoscopy
- Active or planned participation in any other clinical trial or observational study without prior approval from the PI

#### 8.4. Withdrawal Criteria

The investigators, physicians or sponsors may stop the study or remove the subject from the study at any time should they judge that it is in the subject's best interest to do so, if he/she experiences a study-related injury, if the subject needs additional or different medication, or if he/she does not comply with the study plan. They may remove the subject from the study for various other administrative and medical reasons. They can do this without the subject's consent.

# 9. STUDY CONDUCT

#### 9.1. Study Overview

A subject's participation in this study is expected to be approximately 24 weeks. The day the subject begins taking the doxycycline will be designated as day 0 and enrollment. The study will include a bronchoscopy procedure at the enrollment/entry visit and week 12 visit.

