#### ENROLLMENT

- Physical examination including your signs (blood pressure, pulse, and breathing rate) weight and height, and amount of oxygen in the blood
- Lung function tests (lung volumes, spirometry (post bronchodilator))
- Assessment of any side effects or symptoms and if there have been any changes in any of the medications you may be taking
- EKG (optional; repeated only if 30 days have passed since last EKG)
- Blood will be drawn from a vein to check blood counts (to look for infection or anemia), blood chemistries (blood minerals, blood sugar level, kidney and liver function), stored serum and biomarkers
- Urine will be collected to evaluate toxicology for drugs
- Urine will be collected to measure poisonous alkaloid from tobacco and the break-down product of nicotine from cigarette smoke
- For females capable of getting pregnant, urine will be collected to test for pregnancy. If you are pregnant, you will not be allowed to participate in this study
- Study drug dispensing
- Respiratory symptom and smoking questionnaires
- Oral rinse to collect samples of the bacterial communities in the oral mouth and upper airway and to remove loose debris that may contaminate the airway samples.
- Bronchoscopy

#### WEEK 2

- Physical examination including your signs (blood pressure, pulse, and breathing rate) weight and height, and amount of oxygen in the blood
- Lung function tests (lung volumes, spirometry (post bronchodilator) and diffusing capacity of the lung for carbon monoxide [DLCO])
- Assessment of any side effects or symptoms and if there have been any changes in any of the medications you may be taking
- Blood will be drawn from a vein to check blood counts (to look for infection or anemia), blood chemistries (blood minerals, blood sugar level, kidney and liver function), stored serum and biomarkers
- For females capable of getting pregnant, urine will be collected to test for pregnancy. If you are pregnant, you will not be allowed to participate in this study

#### WEEK 6

- Physical examination including your signs (blood pressure, pulse, and breathing rate) weight and height, and amount of oxygen in the blood
- Assessment of any side effects or symptoms and if there have been any changes in any of the medications you may be taking
- Blood will be drawn from a vein to check blood counts (to look for infection or anemia), blood chemistries (blood minerals, blood sugar level, kidney and liver function), stored serum and biomarkers

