#### (4) Risks associated with a fiberoptic bronchoscopy

Fiberoptic Bronchoscopy. [name] group has well established procedures to reduce the risk of bronchoscopies. Potential complications from fiberoptic bronchoscopy include: (1) transient fever within 12 hours of the procedure; (2) bleeding within the nasopharynx due to trauma from passage of the bronchoscope; (3) allergic reactions to any of the pre-medications or local anesthesia; (4) cardiac arrhythmias due either to vagal stimulation or to toxicity of local anesthesia; (5) aspiration pneumonia (the presence of foreign fluid, blood, saliva, or stomach contents in the airways can occur when an individual consumes food prior to the bronchoscopy; as a result of vomiting; this risk is prevented by having all individuals fast for six hours prior to the procedures); (6) lack of oxygen and the associated shortness of breath; and (7) bronchospasm (the narrowing of the windpipes that causes shortness of breath). The most common of these problems are transient fever and bleeding and these are usually self-limiting. The medications used during the bronchoscopy cause drowsiness and may cause the subject's mouth and/or nose to feel dry. Risks associated with the medications include tachycardia and/or a transient lowering of blood pressure, which may be associated with light-headedness, dizziness, nausea, chills, rigors and in rare cases, vomiting. The problems affecting individuals with allergies to the medications used in bronchoscopy may be minimized by excluding individuals with these allergies from protocol. The difficulties with cardiac arrhythmias may be managed and anticipated by continuous cardiac monitoring throughout the procedures. In this context, bronchoscopy with bronchoalveolar lavage and/or bronchial brushing as performed in this manner is a safe procedure.

Since there has been a report of a death associated with fiberoptic bronchoscopy in a normal individual in Rochester, NY (reported in the New York Times, April 3, 1996), it is relevant to discuss the safety issues regarding this procedure and how our group insures the safety of study participants.

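### Does the unanchored ±14-day Entry window in Table II allow the baseline lavage to be collected after study drug has started?

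*Combined protocol and SAP*

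**What the plan says.** - **Day 0.** Section 9.1: "The day the subject begins taking the doxycycline will be designated as day 0 and enrollment". The next sentence reads: "The study will include a bronchoscopy procedure at the enrollment/entry visit and week 12 visit".
- **Drug supply.** The section 7.2 Enrollment list contains "Study drug dispensing" and bronchoscopy at the same visit. The Table I row "Dispense study drug" has no mark before Entry.
- **Windows.** Table II has two rows. The bronchoscopy-visit row gives ±14 days at Entry and at week 12. The row for all other evaluations gives ±7 days at weeks 2, 6, 18 and 24 and at premature discontinuation. No reference day is named for Entry.
- **Research blood.** Footnote 5 of Table I says "Bronchoscopy visits (Week 0/Entry and Week 12), blood samples are collected for: doxycycline blood levels", and separately "Non-bronchoscopy visits: (Week 2, Week 6, and Week 18 and Week 24) blood samples are collected for: doxycycline blood levels".
- **Use of the samples.** Section 6 states the lavage cell numbers, macrophage gene expression, MMP activity, cytokines and bacterial burden as changes. Section 7.1 lists MMP inhibition as a secondary endpoint. The synopsis compares changes from baseline between arms, and its Study Design text calls the first bronchoscopy baseline.

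**The concern.** A change-from-baseline analysis needs a baseline taken before treatment. Here first intake, day 0 and enrollment are one day, the Entry bronchoscopy carries a window running 14 days in both directions, and nothing visible says which comes first, the lavage or the first dose. Day 0 is the only day the protocol defines, so it is natural to count the window from it. On that count, a lavage two weeks into treatment would be within the rules.

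The consequence would be one-directional. Placebo subjects would have a clean baseline whenever it was taken. A doxycycline subject sampled after starting drug would already show part of any effect at baseline, so the measured change would shrink toward zero. Only two lavages are scheduled, so a compromised baseline could not be replaced. With 30 subjects randomized 2:1 there are 20 on doxycycline, and a few such cases could weaken the test of whether the drug inhibits MMP activity in the lung, one of the trial's two overarching hypotheses.

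**Working it through.** **1. Size on the worrying reading (window counted from day 0).**
- Doses scheduled to week 12: 2 per day × 84 days = 168.
- Lavage on day +14: 2 × 14 = 28 doses already scheduled, and 28/168 = 16.7%.

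The effect on results cannot be derived from the documents. As an illustration only, let q be the share of doxycycline subjects with a post-dose baseline and f the share of the drug effect already present then. The observed difference in change is (1 − q·f) times the true one. Assume a two-sided 0.05 test, 20 against 10 subjects, and a true effect with 80% power, which is (1.960 + 0.842) × √(1/10 + 1/20) = 1.085 SD. Power falls to 0.747 at q·f = 0.0625 and to 0.288 at q·f = 0.50. Neither q nor f is in the documents, so the loss matters only if this reading is possible.

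**2. Is that reading possible? Table II against footnote 5.**

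| Visit | Other-evaluations row | Bronchoscopy-visit row | Class in footnote 5 |
|---|---|---|---|
| Entry | N/A | ±14 days | bronchoscopy |
| Week 2 | ±7 days | N/A | non-bronchoscopy |
| Week 6 | ±7 days | N/A | non-bronchoscopy |
| Week 12 | N/A | ±14 days | bronchoscopy |
| Week 18 | ±7 days | N/A | non-bronchoscopy |
| Week 24 | ±7 days | N/A | non-bronchoscopy |

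No visit has a window in both rows, and the split matches footnote 5 exactly. Footnote 5 applies it to whole visits, blood draws included. If the bronchoscopy row covered only the procedure, the spirometry, safety labs and dispensing at week 12 would have no window at all. The row therefore sets a window for the visit.

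**3. What moves with the visit.** Drug is first dispensed at Entry, and section 9.1 puts the bronchoscopy at Entry. If the visit shifts, dispensing, first intake and day 0 shift too. A lavage on day +14 would need a second, separate entry visit, which no part of the schedule provides. It would also collide with week 2: 14 ± 7 gives days 7 to 21, which overlaps days 7 to 14 of the supposed Entry window, and footnote 5 classes week 2 as non-bronchoscopy.

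**4. Interval between lavages.** Section 11.1 (4) puts the second bronchoscopy three months after the first.
- Visit reading: 84 − 14 = 70 to 84 + 14 = 98 days.
- Detached reading: 70 − 14 = 56 to 98 + 14 = 112 days.

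The visit reading stays closer to the stated interval.

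**5. What is left.** Only the order within the Entry day is open. At most one dose could precede a same-day lavage: 1/168 = 0.6%.

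**6. Would such a dose be visible?** Table III gives "Doxycycline blood levels" at 6 visits of 12 mL, and 12 × 6 = 72 mL matches its total. Footnote 5 also names six visits (Entry and weeks 2, 6, 12, 18 and 24), so an Entry level is planned. It would show exposure before the blood draw, though not a dose taken between the draw and the lavage.

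**The case for a change.** The best case for acting is that calling a sample baseline labels it without ordering anything. The Enrollment list names dispensing before bronchoscopy, no rule uses the Entry drug level to confirm a drug-free baseline, and a ± tolerance on the visit that defines day 0 has no clear meaning. The synopsis says the higher dose was chosen to reduce the risk of falsely concluding that the drug has no biological effect, and a loose baseline would leave another route to that error. Clarifying the text would take only a few words.

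Part of this stands. Table II names no reference day, and the same-day order is not written in the text available. That limit matters: section 10 points to a study timeline and section 11.1 (4) to a bronchoscopy operating procedure, neither of which is in the text, and it is unknown whether either settles the order. The same gap reaches the serum inflammatory markers, which are also stated as change and drawn at Entry.

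The 14-day exposure does not stand, because it requires setting aside Table I, footnote 5 and section 9.1. The Enrollment list is not said to be chronological, and dispensing is not intake. Subjects also arrive for the procedure under a precaution of "having all individuals fast for six hours prior to the procedures". That precaution is given for aspiration risk and does not mention study drug, so it supports a pre-dose lavage only weakly.

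Tightening the window to one side would bring its own inconsistency. A range of −14 to 0 days would let the lavage fall on a different day from enrollment, against section 9.1, and would widen the interval between lavages from 70–98 days to 70–112 days.

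**Conclusion.** No change to the plan follows. Table II's Entry window is a visit-level tolerance with an unnamed reference day, which is a clerical omission. Followed as written, the schedule gives a sound baseline. The remaining uncertainty is whether a single dose (1 of 168, 0.6%) could precede a same-day lavage, and it concerns only secondary measures analysed as change. The primary safety/tolerability endpoint and its sample-size reasoning do not depend on it, and neither do the drug-level and resistance-frequency measures, which are not stated as change.

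This rests on two assumptions: that Table II's rows mean whole visits, which their complementary pattern and footnote 5 support, and that staff treat a sample called baseline as one taken before treatment. If records showed Entry lavages on a later day than first intake, the conclusion would need to be revisited; nothing in the documents suggests that.
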